**Document Number: VAL-PRT-0041** 

# 5.10 Stool sample archival

If available, replicate stool samples will be archived for research use. Samples will be deidentified and will be barcoded with the patient's unique identifier for tracking purposes. Specimens will be stored indefinitely or until the entirety of the sample is used. Samples can be stored at Geneoscopy's Laboratories or at a bank that is contracted by Geneoscopy.

#### 5.11 Study Schedule

**Screening survey**: This may occur within 1 day or over a number of days.

- Obtain information
- Determine initial eligibility
- Obtain demographics

**Initial contact from the call center:** This may occur within 1 day or over a number of days.

- Confirm eligibility
- Sign informed consent form
- Sign medical data release form(s)
- Dispense Collection Kit
- Schedule colonoscopy and/or obtain procedure information
- Enter all patient data into the CRO portal

Stool collection: Complete prior to the colonoscopy preparation / procedure

- Subject is instructed to complete the collection prior to colonoscopy preparation and procedure
- Subject collects stool sample and iFOBT swab
- Subject attests to sample collection
- Subject will indicate if a repeat sample collection is necessary and study member will initiate a subsequent collection kit to be sent to the participant's residence

Stool assessment: Completed upon receipt of the stool sample in Geneoscopy's laboratory

- Laboratory technologists will receive collection kit
- Technologists will accession stool samples and iFOBT
- iFOBT will be read
- Sample will be processed using the molecular component of the mt-sRNA test
- Mt-sRNA Test score is generate for the participant
- Study members determine if a repeat stool sample collection is necessary and arranges for subsequent collection kit to be sent to the participant's residence

# Bowel preparation: Must be initiated after stool collection

• Subject performs bowel preparation according to the instructions provided by the facility where the procedure is being performed

# Colonoscopy procedure: Must be initiated after stool collection

- Subject undergoes standard of care screening colonoscopy
- Endoscopist will send any lesions removed during the colonoscopy to histopathology

## **Record retrieval:** Initiated approximately 3 weeks after colonoscopy procedure

- The CRO will call the endoscopy center and provide medical data release forms to obtain colonoscopy and histopathology results
- Reports from the colonoscopy and histopathology will be sent to the CRO

GENEOSCOPY, INC.
-------------------------

**Document Number: VAL-PRT-0041** 

• Data will be entered in the CRO's patient portal

#### Pathology review: Can be completed at any time

- Study member determines if a repeat colonoscopy is needed or if the participant is ineligible based on reports
- Two pathologists independently review the reports
- Algorithm pairs the pathology classifications and determines if a tie-break review, or subsequent review, is necessary

Study termination: Date of obtaining the last report required to meet study criteria

 Study member determines if a repeat colonoscopy is needed or if the participant is ineligible based on reports

## 6. Study Materials and Device Chain of Custody

### 6.1 Sponsor-provided materials

Geneoscopy will contract to manufacture Collection Kits for the study. The contractor will manufacture the kits and distribute kits to the patient once they are enrolled into the study. The contractor will also be responsible for reissuing kits to patients, as needed. Geneoscopy will provide material specifications and bill of materials to the contractor including labeling and packaging information.

### 6.2 Site-provided materials

The individual endoscopy sites will be responsible for ensuring all standard of care requirements for a screening colonoscopy are provided to the patient prior to the procedure. This includes colonoscopy preparation materials, consent forms for the colonoscopy procedure, garments for the procedure, or other items that are required.

#### 6.3 Device Chain of Custody Tracking Procedures

To ensure documentation of the device during manufacturing and transit, records will be kept on all collection kits through the the CRO's portal. In addition to the unique identifier provided by the CRO, two additional unique identifiers will be associated with Collection Kit components. These labels will be affixed to the external box, the stool sample collection bucket, the iFOBT swab, and the attestation form. These labels will be in human readable and barcode format. Barcodes can be scanned once received by the laboratory to ensure receipt. These barcodes will be used to track return of kits following sample collection. Records associating collection kits with samples will be stored in an electronic database that is maintained by the CRO and the Sponsor. Attestation forms will be retained by the Sponsor to confirm data within the electronic database.

#### 7. Potential Risks and Benefits

#### 7.1 Risks

#### **Stool Sample:**

Risks of using the mt-sRNA test are similar to risks associated with other stool-based *in-vitro* diagnostics. Sample collection is performed in the participant's residence, which is comparable to normal methods for waste removal. Risks include misuse of the collection device, and subsequent erroneous result. While there are no known serious risks to collecting stool samples, there may be unknown risks.

		ccc	DV	INC.
CIFI	urc)	SUL	IPY.	HIMU
			,, ,,	

**Document Number: VAL-PRT-0041** 

#### **Colonoscopy**:

Undergoing a colonoscopy has known risks. These risks include gastric distress prior to or after the procedure, perforation of the intestines during the procedure, and/or bleeding during or after the procedure. These risks are disclosed to the participant by the gastroenterologist's office prior to the procedure.

#### **Medical records:**

There is a rare possibility that confidential information about the subject may be accidentally disclosed. This risk is minimized by protections described in the Confidentiality section below and will be managed by the Data Management Plan.

# **Privacy Risks:**

There is a rare risk that genetic research data could be shared with unauthorized users. This would result in the subject being at risk of loss of the privacy of their health data. This risk is minimized by implementing protections such as sample deidentification, use of secure databases, and training for all clinical trial personnel.

#### 7.2 Benefits

There is no direct benefit to subjects from their participation in the study although they may benefit from receiving a colonoscopy. Through this study, subjects will be guided through the colorectal cancer screening process and will therefore be up-to-date with current screening guidelines. It is our hope that, in the future, other people might benefit from this study as we will be able to develop improved diagnostics to detect and prevent colorectal cancer.

### 7.3 Participant Remuneration

The participant will be provided a \$200 gift card for participating in the study. The participant will be paid once the participant completes the study. The participation will be considered complete after the following have been received:

- The genetic sample(s) (stool)
- The completed iFOBT test
- Completed Attestation Form
- Completed Medical Record Release Form(s)
- Medical/clinical information provided during enrollment
- Colonoscopy result with histopathology, if applicable

# 7.4 Study Oversight

The principal investigator listed on the study will be responsible for study oversight. The principal investigator, in conjunction with the Geneoscopy team, will be responsible for monitoring, auditing, IRB review, and regulatory inspection by providing direct access to study related source data. Any required modifications or changes in the scope of the study will be handled by submitting an amendment to the IRB. Geneoscopy will not work outside of the scope of the proposed study unless these amendments are approved by the IRB.

CENTERCORDY INC	Title: CRC-PREVENT Clinical Validation Protocol
GENEOSCOPY, INC.	Document Number: VAL-PRT-00/11

# 8. Data and Safety Monitoring

#### 8.1 Data Management

Various data will be collected from the participant and stored in a secure centralized database. All data will be subject to the Data Management Plan. Data will be obtained from five sources:

**Eligibility Survey:** The responses to the eligibility survey will be obtained from the CRO using a secure API. The following data will be collected:

- If the participant has ever had a colonoscopy
  - o Date of last colonoscopy
  - Outcome of last colonoscopy
- If the participant has a colonoscopy scheduled for the future
  - o Date of future colonoscopy
- Participant's personal history of colon or rectal cancer
- If the participant had a previous diagnosis of disease that increases the participant's risk of colorectal cancer
- If the participant is currently exhibiting gastrointestinal distress
- If the participant has even been screened for colorectal cancer with method other than colonoscopy
  - o If yes, what screening mechanism was used
  - o If yes, when did this take place
- Participant's family history of colorectal cancer
  - o If yes, which family members
- Gender
- Age
- Race / Ethnicity
- Smoking status
- Annual household income
- Insurance type
- Communication information (e.g., email, address, phone)

**Collection Kit Tracking Information**: Sample tracking information will be collected using a courier's online portal. The following data will be collected:

- Date and time that the Collection Kit was shipped to the participant's requested location
- Date and time that the Collection Kit was shipped from participant's requested location to Geneoscopy's Laboratories
- Communication information (e.g., email, address, phone)

**Sample Information**: Data about the sample and collection kit will be obtained. This will be collected by study staff who are accessioning the sample at Geneoscopy's Laboratories. The data will be collected includes:

- Information contained on / within the Collection Kit (e.g., reagent lots and expiration dates, sample IDs)
- Information written on the Collection Kit or collection kit contents that was provided by the participant (e.g., collection time / date, participant date of birth)
- Information on the Attestation forms

GEN				7 I B	
	-()	SU	JPY		ut
9 L I 4	-	-		,	~~ :

**Document Number: VAL-PRT-0041** 

• Information written on the iFOBT

**Sample Processing Information**: During processing at Geneoscopy's Laboratories, data that is generated will be obtained and stored using a secure central database. This includes:

- Data related to sample accession, RNA extraction, and RNA quantification
- RNA concentrations for seRNA biomarkers
- iFOBT data (e.g., Sampling Bottle status, iFOBT test results)

**Clinical Data**: Participant medical reports will be obtained from the participant's physicians. These reports are:

- Colonoscopy reports
- Histopathology reports (Surgical Pathology)
- History and Physical
- Physician notes
- Patient labels from processing colonoscopy / histopathology reports

#### 8.2 IRB Review, Ethics, and Informed Consent

The protocol, informed consent document, and relevant supporting information must be submitted to the IRB for review and must be approved before the study is initiated. In addition, any subject recruitment materials must be approved by the IRB prior to being used. This study will be conducted in accordance with the ethical principles that have their origin in the Declaration of Helsinki and that are consistent with Good Clinical Practice and applicable regulatory requirements. Geneoscopy must submit any change to the protocol to the IRB for review and approval before implementation. A protocol change intended to eliminate an apparent immediate hazard to subjects may be implemented immediately and the reviewing IRB are notified within 10 working days.

It is the responsibility of the investigator to provide each subject with full and adequate verbal and written information using the IRB approved informed consent document, including the objective and procedures of the study and the possible risks involved before inclusion in the study. Verbal informed consent must be obtained prior to performing any study-related procedures, including a screening colonoscopy. A copy of the informed consent document must be provided to the study subject.

Investigators must provide a *curriculum vitae* (CV) to the IRB for review of credentials. The investigator and required study members must also provide the following, as needed:

- Financial disclosures
- Medical license, as needed
- Correspondence to IRB

#### **8.3** Confidentiality

To help protect confidentiality, samples will not have any name or address on it; they will be labeled with a code in order to protect health information and identity. The specimen(s) will be stored in freezers in a locked laboratory at Geneoscopy's Laboratories. All coded specimens will be linked to study participants on a separate master list, which will be stored in a locked cabinet (the study coordinators have the only key), in a password protected file, or in a secure database. Specimens can be stored indefinitely. If a report or article about this study is written or the study data are shared with others, we will do so in such a way that participants cannot be directly identified.

**Title:** CRC-PREVENT Clinical Validation Protocol

**Document Number: VAL-PRT-0041** 

#### 8.4 Intended Use of Data

This study will work towards validating a non-invasive screening test that will assess risk for colorectal neoplasias. The added benefits to society will be to increase patient compliance, reduce the cost of healthcare, and provide better healthcare for patients.

#### 8.5 Safety Monitoring

There are no known risks to collecting stool samples, though there may be unknown risks. If subjects do experience an Unanticipated Adverse Device Effect (UADE) during the collection of the stool sample, they are prompted to contact the study team as soon as possible. A UADE is any serious adverse effect on health or safety, any life-threatening problem or death caused by, or associated with a device, if that effect, problem, or death was not previously identified in nature, severity, or degree of incidence in the application; or any other unanticipated serious problem associated with a device that relates to the rights, safety, or welfare of subjects.

Non-serious Adverse Events (concerns, complaints, etc.) will also be recorded and maintained by the the CRO call center. Complaints will be entered into the online portal by the study member who receives the complaint.

#### 8.6 Record Retention

The Sponsor and all associated parties must maintain records for at least 2 years after the termination of the investigation. Written approval from the Sponsor must be obtained prior to destruction of any study records. All sites are subject to investigation by the Sponsor, or other regulatory agencies that inspect study records. These inspections are meant to verify adherence to all study protocols.

#### 8.7 Protocol Deviations

A deviation is defined as a change, departure, or alteration to the procedures of the research protocol that diverges from the procedures that are approved by the IRB. Upon discovery of a deviation, the Principal Investigator is responsible for reporting the deviation to the IRB, as required. Deviations must be entered into the online portal and reporting associated with deviations must be assessed during assessment of primary and secondary endpoints.

CENTOSCODY INC	Title: CRC-PREVENT Clinical Validation Protocol
GENEOSCOPY, INC.	Document Number: VAL-PRT-0041

## 2. Abbreviations and Definitions

iFOBT / FIT	Fecal occult blood test / Fecal immunochemical test
IFU	Instructions for use
seRNA	Stool-derived eukaryotic RNA
CSR	Clinical Study Report
CRC	Colorectal cancer
AA	Advanced adenoma
OA	Other precancerous adenomas
FDA	Food and drug administration
SSA	Sessile serrated adenoma/polyp
TA	Tubular adenoma
VA	Villous adenoma
TVA	Tubulovillous adenoma
IRB	Institutional review board
Sen	Sensitivity
Sp	specificity
SOP	Standard operating procedure
ICF	Informed consent form
CSR	Clinical Study Report
SAP	Statistical Analysis Plan

Title: CRC-PREVENT Statistical Analysis Plan

**Document Number:** CT-PLN-0002

#### 3. Introduction

#### 3.1 Preface

Colorectal cancer (CRC) is the third most common cancer in both men and women in the United States, the second deadliest cancer globally, and accounted for over 50,000 deaths in 2018 in the US alone. Disease onset is typically insidious, starting as a small polyp which can take several years to further accrue somatic mutations and develop into an invasive carcinoma. If detected early, CRC has a five-year survival rate of 92%. However, 63% of newly diagnosed patients have advanced disease, with an associated five-year survival rate as low as 14%. Late-stage diagnosis typically results from patient noncompliance with screening guidelines, indicating that these cancers could have been detected earlier by following standard of care recommendations. CRC screening compliance has remained stagnant over the past 20 years and is currently estimated to be approximately 60%. Historically, low compliance rates have been due to the inconvenience, unpleasantness, and perceived hazards of colonoscopies.

While colonoscopies are currently the gold-standard for colorectal cancer screening, the procedure does have associated risks to the patient. A colonoscopy procedure can result in an adverse event, which includes: pain (2.59%), hemorrhage (0.28%), perforation (0.05%). These complications can lead to hospitalization (1.17%), urgent care visit (2.34%), or in rare cases death (0.01%). An additional risk to the patient is a false negative result. It has been described that colonoscopies can miss 15-24% of all adenomas, 6-11% of advanced adenomas, and 1% of carcinomas.

While many noninvasive tests have been developed to address compliance issues, none compare to the diagnostic accuracy of a colonoscopy. Currently, the most accurate noninvasive diagnostic (Cologuard, Exact Sciences) cites a CRC sensitivity of 92%, however, the advanced adenoma (AA) detection rate for this test is only 42%. Other noninvasive stool-based tests include the fecal occult blood test and the fecal immunochemical test (FIT), which use lateral flow for detection of blood in stool. These alternatives can be highly sensitive (79%) and specific (94%) for CRC, but have AA sensitivities of less than 30%. Accurate detection of precancerous adenomas would allow for preemptive excision of dysplastic tissue prior to carcinogenesis, thus reducing CRC incidence and the associated morbidity and mortality.

Geneoscopy has developed a multi-factor stool-RNA (mt-sRNA) assay that combines 8 stool-derived eukaryotic RNA (seRNA) biomarkers, patient demographic information (smoking status), and a fecal immunochemical test (FIT / iFOBT) to sensitively detect CRC, AA, and other precancerous adenomas. The mt-sRNA assay is undergoing analytical and clinical validation through a clinical trial entitled, CRC-PREVENT (NCT04739722). The results from CRC-PREVENT will be analyzed using the statistical analysis plan outlined in this document to assess safety and efficacy of the mt-sRNA assay.

## 3.2 Scope of the Analyses

The scope of the statistical analysis plan is to use the data from the CRC-PREVENT clinical trial to assess the safety and efficacy of the mt-sRNA assay produced by Geneoscopy. Specifically, results from the mt-sRNA test will be compared to results from a colonoscopy to ascertain sensitivity for positive lesions and specificity for negative lesions. Results from these analyses will be included in the clinical study report (CSR).

GENEOSCOPY,	INC.

Title: CRC-PREVENT Statistical Analysis Plan

**Document Number:** CT-PLN-0002

#### 4. Study Objectives and Endpoints

#### 4.1 Primary Study Objectives

The primary objective of this study is to determine safety and efficacy of Geneoscopy's mt-sRNA test for detection of colorectal neoplasias (i.e., colorectal cancer and advanced adenomas) using colonoscopy as the reference method. Lesion categories will be confirmed by histopathologic examination. Performance of the mt-sRNA test will be evaluated based on comparison of the mt-sRNA result with the histopathological category. The primary objectives will support clinical claims to be used in regulatory submissions. If acceptance criteria are met, findings pertaining to all primary and secondary objectives will be reported to the clinical community through academic presentations and in a peer-reviewed publication.

#### 4.2 Study Endpoints

The primary objective of this study is to determine the ability of Geneoscopy's mt-sRNA test to detect colorectal neoplasias (i.e., colorectal cancer and advanced adenomas) when using colonoscopy as the reference method. Colonoscopy reports are assessed by verified pathologists to determine subject categories. The subject categories (see **Table 1**) are compared to the mt-sRNA test result (Positive or Negative) to assess primary and secondary outcomes.

Table 1. Methods for classifying study subjects into categories based on colonoscopy findings.

Category	Binary Category	Description
Colorectal Cancer (CRC)	Positive	Stage I-IV colorectal cancer, any size
Advanced Adenomas (AA)	Positive	High-grade dysplasia or ≥10 adenomas, any size Tubulovillous adenoma, any size Tubular adenoma, ≥10mm Traditional serrated adenoma, ≥10mm
Medium Risk Adenomas (MRA)	Negative	Hyperplastic polyp or SSL, ≥10mm 5-9 adenomas (TA + SSL), <10mm 3-4 adenomas (TA + SSL), <10mm
Low Risk Adenomas (LRA)	Negative	1-2 adenomas (TA + SSL), 5-9mm 1-2 adenomas (TA + SSL), <5mm
No Findings (NEG)	Negative	Hyperplastic polyps, <10mm Benign lesions, any size No lesions on colonoscopy

#### 4.2.1 Primary Study Endpoints

The primary objective of this study will be assessed using four co-primary performance measures or study endpoints:

• mt-sRNA test sensitivity for subjects with colorectal cancer (CRC), which is the percentage of individuals with a diagnosis of colorectal cancer (**Table 1**) that were detected as positive by the mt-sRNA test.

	Title: CRC-PREVENT Statistical Analysis Plan
GENEOSCOPY, INC.	Document Number: CT-PLN-0002

- mt-sRNA test sensitivity for subjects with advanced adenomas (AA), which is the percentage of individuals with a diagnosis of advanced adenoma (**Table 1**) that were detected as positive by the mt-sRNA test.
- mt-sRNA test specificity for subjects with negative findings, which is the percentage of individuals with a diagnosis of benign polyps, or no findings on a colonoscopy (**Table 1**) that were detected as negative by the mt-sRNA test.

Criteria for success for these metrics requires the following:

- With regards to the mt-sRNA test sensitivity for subjects with CRC, the sensitivity of CRC must be greater than 90% and the lower bound of the 95% two-sided confidence interval must be greater than 80%.
- With regards to the mt-sRNA test sensitivity for subjects with AA, the sensitivity of AA must be greater than 45% and the lower bound of the 95% two-sided confidence interval must be greater than 40%.
- With regards to the mt-sRNA test specificity for subjects with no findings on a colonoscopy, the specificity must be greater than 80%.

#### 4.2.2 Secondary Study Endpoints

The primary objective of this study will also be assessed using four co-secondary performance measures or study endpoints:

- mt-sRNA test sensitivity for subjects with high-grade dysplasia, which is the percentage of individuals with a diagnosis of carcinoma *in situ* or advanced adenoma with high grade dysplasia (**Table 1**) that were detected as positive by the mt-sRNA test.
- mt-sRNA test sensitivity for subjects with villous / tubulovillous adenomas, which is the percentage of individuals with a diagnosis of advanced adenoma with villous or tubulovillous growth pattern, any size (**Table 1**) that were detected as positive by the mt-sRNA test.
- mt-sRNA test sensitivity for subjects with sessile serrated adenomas / polyps, which is the percentage of individuals with a diagnosis of hyperplastic polyps or sessile serrated adenoma / polyp (SSA) ≥ 10mm any size (**Table 1**) that were detected as positive by the mt-sRNA test.

For each of these metrics, the two-sided 95% exact binomial confidence intervals will be provided.

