# 2. Objectives

#### 2.1 Primary and Secondary Objectives

The primary objective of this study is to determine the sensitivity and specificity of Geneoscopy's mt-sRNA test for colorectal neoplasias (i.e., colorectal cancer and advanced adenomas) using colonoscopy as the reference method. Lesion categories will be confirmed by histopathologic examination. Performance of the mt-sRNA test will be evaluated based on comparison of the mt-sRNA test result with the histopathological category (**Table 1**). The primary objectives will support clinical claims to be used in regulatory submissions. If acceptance criteria are met, findings pertaining to all primary and secondary objectives will be reported to the clinical community through academic presentations and in a peer-reviewed publication.

Four co-primary performance measures are specified as:

- mt-sRNA test sensitivity for subjects with colorectal cancer (CRC), which is the percentage of individuals with a diagnosis of colorectal cancer (**Table 1**) that were detected as positive by the mt-sRNA test.
- mt-sRNA test sensitivity for subjects with advanced adenomas (AA), which is the percentage of individuals with a diagnosis of advanced adenoma (**Table 1**) that were detected as positive by the mt-sRNA test.
- mt-sRNA test specificity for subjects with negative findings, which is the percentage of individuals with a diagnosis of benign polyps, or no findings on a colonoscopy (**Table 1**) that were detected as negative by the mt-sRNA test.

CENEOCCODY INC	Title: CRC-PREVENT Clinical Validation Protocol
GENEOSCOPY, INC.	Document Number: VAL-PRT-0041

There will also be three co-secondary performance measures:

- mt-sRNA test sensitivity for subjects with high-grade dysplasia, which is the percentage of individuals with a diagnosis of carcinoma *in situ* or advanced adenoma with high grade dysplasia (**Table 1**) that were detected as positive by the mt-sRNA test.
- mt-sRNA test sensitivity for subjects with villous / tubulovillous adenomas, which is the percentage of individuals with a diagnosis of advanced adenoma with villous or tubulovillous growth pattern, any size (Table 1) that were detected as positive by the mt-sRNA test.
- mt-sRNA test sensitivity for subjects with sessile serrated adenomas / polyps, which is the percentage of individuals with a diagnosis of hyperplastic polyps or sessile serrated adenoma / polyp (SSA) ≥ 10mm any size (Table 1) that were detected as positive by the mt-sRNA test.

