#### 9.3 Analysis for Secondary Study Endpoints

For Secondary Study Endpoints, a variety of categorical data analysis methods will be used to analyze the results from the Mt-sRNA test and the reference colonoscopy results. Binomial proportions together with exact 95% confidence intervals will be used to summarize sensitivity and specificity for various categories. Fisher exact tests will be used for determining whether there are significant differences in assay performance between various subgroups, e.g., are there differences in sensitivity for CRC between females and males. If there are statistically significant ( $\alpha$ =0.05) differences observed, logistic regression will be used to perform any modeling to better understand differences.

**Table 8.** Performance Characteristics by Cancer Stage

Subtype	CRC Stage	CRC Sensitivity	95% confidence Interval
Category 1.0	Stage 0	n = X $n/N (%)$	95% CI
	Stage I	n = X $n/N (%)$	95% CI
	Stage II	n = X $n/N (%)$	95% CI
	Stage III	n = X $n/N (%)$	95% CI
	Stage IV	n = X n/N (%)	95% CI

GENEOSCOPY, INC.	Title: CRC-PREVENT Statistical Analysis Plan		
	Document Number: CT-PLN-0002		
p-value			

**Table 9.** Performance Characteristics by Lesion / Advanced Adenoma Subtype

Subtype	Lesion Type	Sensitivity	95% confidence interval
Category 2.1	high-grade dysplasia / carcinoma in-situ	n = X n/N (%)	95% CI
Category 2.2	villous / tubulovillous	n = X $n/N (%)$	95% CI
Subset of category 2.2 + Category 3.1	sessile serrated adenomas / polyps	n = X n/N (%)	95% CI
p-value			

The secondary endpoint metrics will be calculated as:

- mt-sRNA test sensitivity for subjects parsed by cancer staging (Stage 0 Stage IV) based on relevant guidelines.
- mt-sRNA test sensitivity for subjects with high-grade dysplasia / carcinoma in-situ
- mt-sRNA test sensitivity for subjects with villous / tubulovillous adenomas
- mt-sRNA test sensitivity for subjects with sessile serrated adenomas / polyps

If any differences are noted between any categories in the subgroup analyses, logistic regression will be used for further exploration to understand the cause of the differences.

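### The secondary serrated-lesion endpoint carries two incompatible size rules, and SAP Table 9 reports it on a different, partly undefined set of subjects

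*SAP*

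**What the plan says.** Four places describe the endpoint.

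- **Protocol 2.1** counts subjects with "hyperplastic polyps or sessile serrated adenoma / polyp (SSA) ≥ 10mm any size" and refers to Table 1. **SAP 4.2.2** repeats the definition, as a "diagnosis of hyperplastic polyps or sessile serrated adenoma / polyp (SSA) ≥ 10mm any size", also with a reference to Table 1.
- **Table 1** (the same in both documents) has one row that pairs the two lesion types: "Hyperplastic polyp or SSL, ≥10mm", under Medium Risk Adenomas. Smaller lesions sit elsewhere. "Hyperplastic polyps, <10mm" is in No Findings, and small sessile serrated lesions are in the medium- or low-risk rows by number and size, for example "1-2 adenomas (TA + SSL), 5-9mm".
- **SAP Table 9** builds the reported row from "Subset of category 2.2 + Category 3.1". The row above it labels category 2.2 "villous / tubulovillous".
- **The SAP 9.3 metric list** says only "mt-sRNA test sensitivity for subjects with sessile serrated adenomas / polyps".

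SAP 4.2.2 promises exact 95% confidence intervals for the secondary endpoints. Neither document sets an acceptance limit for this one.

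**The concern.** A sensitivity is defined by its denominator, and here the denominator depends on which sentence the analyst follows. The endpoint text states two size rules at once. The reporting table adds part of the advanced-adenoma group without saying which part. The metric list drops both the size limit and one of the two lesion types.

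Two consequences go beyond wording. Under the *any size* words, subjects whose worst finding is a hyperplastic polyp below 10 mm would enter this sensitivity, where a positive test is a success. The same subjects are in No Findings, the denominator of the co-primary specificity in SAP 9.1, where a positive test is an error. Following Table 9 instead mixes in some advanced-adenoma subjects, a group the test is built to call positive.

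**Working it through.** The plan states no expected rate, count, power or limit for this endpoint, so there is no figure of its own to reproduce. The check is a comparison of texts, followed by an illustration on assumed inputs.

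**1. Size rule.** I read SSA in the endpoint and SSL in Table 1 as the same lesion.

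| Place | Size | Hyperplastic polyps | Advanced-adenoma subjects |
|---|---|---|---|
| Protocol 2.1, SAP 4.2.2 | ≥10 mm and any size | included | not mentioned |
| Table 1 row | ≥10 mm | included | no |
| SAP Table 9 | by category only | through 3.1, if that is the Table 1 row | part of 2.2, rule not given |
| SAP 9.3 list | none stated | not mentioned | not mentioned |

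**2. What category 3.1 is.** Table 1 prints no subcategory numbers, although Protocol 5.9 says subcategories come from it. In SAP Table 6 the first line of category 3 is hyperplastic polyp or SSL ≥10 mm, so row order makes that line 3.1. This is an inference. The two documents do not number the categories alike: negative subjects are category 6 in Protocol 5.9 and category 5 in SAP Table 6.

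**3. What the category 2.2 subset could be.** Two readings can be tested.

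- *Serrated lesions within the advanced-adenoma group.* The only such type in Table 1 is traditional serrated adenoma. It is the fourth line of that group, whereas Table 9 labels 2.2 as villous / tubulovillous, which is the second line. Its size rule also differs within the SAP: ≥10 mm in Table 1, any size in Table 6.
- *Villous or tubulovillous subjects who also have a large serrated lesion.* Protocol 5.9 assigns each subject by the most significant lesion, so such a subject would be in category 2. Bringing these subjects back would make sense, but no such rule is written.

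On either reading, subjects taken from 2.2 as Table 9 labels it would stand in two rows of that table.

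**4. Illustration (assumed inputs; not an estimate for this trial).**

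- Subjects: 8,500, the starting sample size in both documents.
- Lesions ≥10 mm: assumed in 3% of subjects (range 1% to 5%), with 40% test-positive (range 25% to 60%).
- Small hyperplastic polyps: the feasibility share in Protocol 1.2, 74/366, with all of them assumed below 10 mm and 20% positive. The 20% reads the reported 80% as the share called negative.
- Category 2.2 subset: assumed to be 10% to 50% of the ≥10 mm count, with 60% positive.

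Middle case:

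- ≥10 mm: N = 0.03 × 8,500 = 255; 102/255 = 40.0% (95% CI 33.9 to 46.3).
- Any size, adding only small hyperplastic polyps: 8,500 × 74/366 ≈ 1,719, of whom 344 positive; (102 + 344)/(255 + 1,719) = 446/1,974 = 22.6% (20.8 to 24.5).
- Table 9 with a subset of 26: (102 + 16)/(255 + 26) = 118/281 = 42.0%. With a subset of 128: (102 + 77)/(255 + 128) = 179/383 = 46.7%.

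Over the full assumed range, the ≥10 mm reading gives about 25% to 60% on 85 to 425 subjects. The any-size reading gives about 20% to 28% on 1,804 to 2,144 subjects. This shows only that the readings are not interchangeable.

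**The case against.** The best defence is that the definition ends with a pointer to Table 1. Only one row there pairs hyperplastic polyps with serrated lesions, and it has the 10 mm floor. The preceding bullet, on villous lesions, ends with the words any size, so a carried-over phrase is the likely cause. Row order makes category 3.1 the same ≥10 mm line, so the core of Table 9 agrees. The overlap with the specificity denominator is itself evidence that *any size* was never meant. All of this stands, and it settles the probable intent of SAP 4.2.2. It does not settle Table 9, where the added subset has no rule, or the unrestricted wording in 9.3.

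A reader might infer three equally live definitions. The documents do not support that: they favour ≥10 mm, and the open question is mainly the category 2.2 addition. That addition may be deliberate, so striking it without asking its purpose would be wrong.

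A reader might also infer that the choice can be made freely once results are known. That goes too far. SAP 5.1, 5.3 and 7.2 lock eligibility and colonoscopy categories before unblinding, and the merged data go to a separate statistical team. Locking does not say which categories are pooled for this endpoint, so some freedom remains.

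**Conclusion.** The endpoint is wrong as written and needs correction in both documents. The size rule contradicts itself, although Table 1 points to ≥10 mm. Table 9 uses a different set with an undefined part, and SAP 9.3 matches neither.

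The effect on the estimate cannot be computed from the documents. The middle-case figures of 40.0%, 22.6% and 42.0% to 46.7% rest wholly on assumed prevalences and positivity rates.

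The importance is modest. The success criteria in Protocol 2.1 and SAP 4.2.1 cover only CRC sensitivity, advanced-adenoma sensitivity and specificity, and the sample size rests on CRC cases. It would be a mistake to infer that the trial's primary conclusion is at risk: the co-primary specificity is clearly defined on No Findings in SAP 9.1, whichever serrated reading is used. What is at stake is a secondary result that SAP 4.1 intends for publication if the acceptance criteria are met.

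**What to change.** Before unblinding:

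1. In Protocol 2.1 and SAP 4.2.2, delete the words any size, so that the endpoint is hyperplastic polyp or SSL ≥10 mm as in Table 1.
2. Print the subcategory numbers in Table 1 of both documents.
3. Use the same wording in the SAP 9.3 metric list.
4. Make the serrated row of SAP Table 9 that one Table 1 category.
5. If the category 2.2 subset is intended, for example advanced-adenoma subjects who also have a serrated lesion ≥10 mm, write the rule in SAP 4.2.2 and report those subjects on a separate line.

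If unblinding has already occurred, report the result under each reading and label the choice as post hoc.

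The cost is wording in two documents, numbering in one table and a change to one table row. No new data or subjects are needed.
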